### **3.3. Study Site**

Preah Vihear is one of the most remote and isolated provinces in Cambodia. The province has a population of around 172,000 people spread out through 293 villages in eight districts. The mainly rural population survive on sustenance farming. Within the province there are 28 government HC, 17 HP, and one referral hospitals. Each HC and HP serves a number of villages and is the first point of access for health care. There are approximately 5,300 recorded deliveries in the province per year (data obtained from PVH provincial health offices).

## **4. OBJECTIVES AND OUTCOME MEASURES**

Objectives	Outcome Measures	Time point(s) of evaluation of this outcome measure (if applicable)
Primary Objective The design, implementation and assessment of a comprehensive community neonatal health package utilising medical and social interventions	A comprehensive community neonatal health package utilising medical and social interventions	Study end
Secondary Objective Reduction of perinatal mortality in PVH province, Cambodia	A one third reduction in perinatal mortality in PVH province, Cambodia	Study end
Tertiary Objectives: To describe the characteristics of neonates born in PVH province, Cambodia over a five-year time period	A document that describes characteristics of neonates, born in PVH province, Cambodia over a five-year time period	Study end
To develop a tool to undertake a full review of neonatal services and capabilities in PVH province, Cambodia 
 
a. Assess the level of knowledge possessed by health care workers with respect to fundamental areas of care surrounding delivery and the neonatal period
 
b. Evaluate current practice regarding delivery and neonatal care
 
c. Undertake a review of health centre facilities and resources
 
d. Record the staff composition and working patterns
 
e. Detect commonalities as well as differences between facilities
 
f. Assess the local community service provision, including the activity of the VHSGs as well as any other community health projects and initiatives
 
	A user-friendly tool to assess neonatal healthcare services A report detailing neonatal services and capabilities in PVH province, Cambodia	Study end

g. Identify factors that may be functioning as barriers and facilitators to improvements in the delivery of care
		

Design a fully comprehensive neonatal healthcare and implementation package adapted to local need
 
a. Provide health workers with essential knowledge with respect the neonatal period.
 
b. Design a programme to teach that is acceptable and feasible for government health workers
 
c. Empower healthcare providers to make positive changes in order to overcome any barrier to improvement.
 
d. Equip each facility with the resources required to safely resuscitate a neonate and provide ongoing neonatal care as required.
	
A locally appropriate neonatal healthcare training and implementation package
	
Study end

Establish VHSG groups to address areas of concern for the local community with respect to childbirth and the neonatal period
 
a. To identify issues communities, have in relation to neonatal health, and which interventions are seen as priorities to improve neonatal health care
	
Frequency and attendance rate of participants at the programmes meetings
	
Study end

With the Kingdom of Cambodia, Ministry of Health and the Provincial Health Director of PVH province develop a programme blueprint and implementation strategy for introduction of the developed programme into other locations within Cambodia
	
A programme and implementation plan for the reduction of neonatal mortality that can be used throughout Cambodia
	
Study end

To calculate the cost-effectiveness of a neonatal community health programme and the resulting changes in care, as compared to the existing care given in the region.		
---	--	--

## 5. STUDY DESIGN

A cluster randomised study design will be used, with a cluster being defined as a HC administrative group, as defined by the PVH Provincial Health Department. This includes all HC, HP, villages, and villagers in that group.

Pilot: to begin in July 2018, consisting of 4 clusters.

Intervention arm: to begin October 2019, consisting of 10 clusters.

Control arm: all remaining clusters.

Completion: December 2022.

The SBLP will be introduced into the provincial referral hospital during 2018.

The SBLP will be introduced into the new referral hospital during 2022.

The choice of which health centres will be included at each time point will be made using purposive sampling to ensure a mix of health centre characteristics. Characteristics that will be taken into account are the distance from the health centre to the referral hospital and number of villages the HC serves.

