## 1. SYNOPSIS

Study Title	Design, implementation and assessment of a comprehensive community neonatal health package utilising medical and social interventions	
Internal ref. no.	N/A	
Study Design	Cluster randomised control trial	
Study Participants	The population of Preah Vihear (PVH) province, Cambodia	
Planned Sample Size	
 
293 villages with 586 Village Health Support Group Workers (VHSG)
 
26,500 children born in Preah Vihear over the study period and their parents (5,300 deliveries a year)
 
306 health centre nurses and midwives from 28 health centres and 17 health posts in Preah Vihear
 
30 nurses, 27 midwives and 18 doctors from Preah Vihear Referral Hospital
 
	
Planned Study Period	5 years	
	Objectives	Outcome Measures
Primary	The design, implementation and assessment of a comprehensive community neonatal health package utilising medical and social interventions	A comprehensive community neonatal health package utilising medical and social interventions
Secondary	Reduction of perinatal mortality in PVH province, Cambodia	A one third reduction in perinatal mortality in PVH province, Cambodia
Tertiary	To describe the characteristics of neonates, born in PVH province, Cambodia over a five-year time period	A document that describes the characteristics of neonates, born in PVH province, Cambodia over a five-year time period
	To develop a tool to undertake a full review of neonatal services and capabilities in PVH province, Cambodia	A user-friendly tool to assess neonatal healthcare services A report detailing neonatal services and capabilities in PVH province, Cambodia
	Design a fully comprehensive neonatal healthcare training and implementation package adapted to local need	A locally appropriate neonatal healthcare training and implementation package
	Establish regular VHSG meetings to address areas of concern for the local community with respect to childbirth and the neonatal period	Frequency and attendance rate of participants at the programmes VHSG group meetings

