#### **Health Care facilities**

Up to two-thirds of neonatal deaths could be prevented if neonates were given proper care during and immediately after birth, because the majority of neonatal deaths occur around the time of delivery [19]. Training primary level health care workers to deal with emergency situations that occur around the time of delivery, such as ante-partum and post-partum haemorrhage, umbilical cord prolapse and shoulder dystocia, has been shown to decrease maternal mortality and neonatal mortality [20]. Similarly, a model for neonatal care in low-resource settings, special baby care areas, has been proven to significantly reduce neonatal mortality over a period of a few years [9].

It is reported that 79% of deliveries in Cambodia occur in healthcare facilities [21]. The majority of these will occur at primary healthcare facilities (health centres (HC) or health Posts (HP)). Babies born in HCs or

HPs who require further care are referred to the referral hospital. The majority of referral hospitals in Cambodia do not have the resources or skills to effectively deal with neonatal complications for babies born either in health centres or in their on-site maternity wards.

The Saving Babies Lives Programme will be developed in partnership with the Kingdom of Cambodia Ministry of Health (MoH). The programme will be approved by the MoH and a memorandum of understanding signed with the provincial health director of Preah Vihear (PVH) province. The major objective of this project is to develop a programme blueprint and implementation strategy for introduction of the developed programme into other locations within Cambodia. Data will be collected and used to assess the impact of the programme, its perceived facilitators and barriers and its successes and failures. This information will be used to iterate the programme content and structure in order to improve it.

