### **Economic Evaluation**

A detailed cost analysis will be carried out to estimate the added resources that are required for the SBLP as compared with standard care. These costs will be combined with estimates for the incremental cost of caring for children at AHC, and HCs if attendance is found to increase, and by modelling the subsequent survival benefits in terms of incremental disability adjusted life years averted. This will indicate whether the SBLP is as cost-effective as compared to the existing standard of care (control arm).

At the time of the newborn health questionnaire, the mother will be asked about any health seeking costs the family incurred for their infant in the first four weeks of life.

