## 6. PARTICIPANT IDENTIFICATION AND RECRUITMENT

### 6.1. Saving Babies Lives Training Programme

#### 6.2. Study Participants

The Saving Babies Lives Programme will be aimed at government health care staff working in the community (VHSG), at HC (nurses and midwives) and at the referral hospital (doctors and nurses)

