#### **Sample size Calculation**

With perinatal mortality rate and a simple parallel cluster randomised trial design, the number of clusters are fixed to the intervention and control arm clusters and the time-frame is fixed to five years. The change in study design has been necessitated by logistical reasons and the post-study power calculations are not relevant. We will report limitations to the power in write-up.

The statistical analysis will remain broadly the same, with the main difference being that we will no longer adjust for the confounding effects of time. The primary analysis will exclude pilot cluster results, and will only be conducted on the intervention and control arm clusters.

Please see the study Statistical Analysis Plan for full details.

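### The control arm very probably refers to a hospital already running the SBLP, so calling it existing or normal care mislabels the comparator and may set whole-package cost against part-package benefit

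*Protocol*

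**What the plan says.** **The programme has a hospital part.** The hypothesis in section 3.1 runs from village to referral hospital. Section 6.2 lists the health staff addressed as those "at HC (nurses and midwives) and at the referral hospital (doctors and nurses", and the Synopsis counts "30 nurses, 27 midwives and 18 doctors from Preah Vihear Referral Hospital".

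**That part starts before the arms are compared.** Section 5: "The SBLP will be introduced into the provincial referral hospital during 2018". The intervention arm of 10 clusters begins in October 2019, and completion is December 2022. A cluster consists of HCs, health posts (HPs), villages and villagers, so the hospital belongs to no arm. Section 5 adds: "The SBLP will be introduced into the new referral hospital during 2022".

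**One hospital is described.** Section 3.3: "Within the province there are 28 government HC, 17 HP, and one referral hospitals". Under Health Care facilities in section 3, babies born in HCs or "HPs who require further care are referred to the referral hospital".

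**The mortality analysis compares the arms.** Section 8.1, Sample size Calculation, says the primary analysis "will only be conducted on the intervention and control arm clusters".

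**The economic comparator is labelled differently.** Section 3.2 judges cost-effectiveness "as compared to the existing standard of care (control arm"). Section 8.1 makes the same identification with the word normal, and section 4 compares with care already given in the region. Both economic paragraphs cost the extra resources of the SBLP without separating the hospital part. On downstream care, section 3.2 counts Angkor Hospital for Children (AHC) and the HCs, while section 8.1 counts the referral hospital.

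**The concern.** A hospital serving both arms is a legitimate background for a cluster trial, provided that costs, effects and the name of the comparator all refer to the same contrast. Here they do not clearly do so. The effect side is a between-arm difference, and both arms appear to have an SBLP hospital. The cost side is written for the programme as a whole. The label says care without the programme.

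Two things are at stake. First, the cost per DALY could put the cost of a village-to-hospital package over a benefit that reflects mainly its HC and village parts. Second, the project's stated purpose is a blueprint for other places in Cambodia. A planner elsewhere would read the result as SBLP against ordinary care, although the contrast presupposes a referral hospital that already has the programme.

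**Working it through.** The protocol states no cost, cost-effectiveness ratio or hospital effect, so there is no planned figure to reproduce. The check is a timeline followed by labelled illustrations.

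**1. Timeline (section 5).**
- Comparison period, October 2019 to December 2022: 3 + 36 = 39 months.
- Hospital SBLP is introduced by the end of 2018, so at least January to September 2019, 9 full months, lie between it and the arm start.
- On these dates no part of the comparison has a provincial referral hospital without the SBLP.
- SBLP enters the new hospital in 2022. October 2019 to December 2021 is 3 + 24 = 27 months, so 27 of the 39 precede that year. Its opening date and catchment are not given, so this does not show how many births it affects.

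**2. What the contrast estimates.** Write H for hospital SBLP and C for HC and village SBLP. With one shared hospital, the intervention arm has H + C and the control arm has H. The difference is C given H. SBLP against care without it would be H + C against neither, and no arm supplies the second term.

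**3. Cost side (share assumed).** Let h be the hospital share of total SBLP cost. The cost that differs by arm is 1 − h. If all hospital cost is charged to the intervention, the ratio is multiplied by 1/(1 − h). If only a 10/28 share is charged (28 equal clusters assumed), the factor is [(1 − h) + h × 10/28]/(1 − h).

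| h | all charged | 10/28 charged | none charged |
|---|---|---|---|
| 10% | 1.11 | 1.04 | 1.00 |
| 25% | 1.33 | 1.12 | 1.00 |
| 50% | 2.00 | 1.36 | 1.00 |

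Staff numbers in the Synopsis give a crude idea of h. Hospital staff: 30 + 27 + 18 = 75. HC and HP staff in 10 of 28 clusters: 306 × 10/28 = 109.3. Village Health Support Group (VHSG) workers: 586 × 10/28 = 209.3.
- Facility staff only: h = 75/(75 + 109.3) = 40.7%, factor 1.69.
- With VHSG workers: h = 75/(75 + 109.3 + 209.3) = 19.1%, factor 1.24.
- Section 6.2 names only doctors and nurses at the hospital. Without the 27 midwives (48 staff) the factors are 1 + 48/109.3 = 1.44 and 1 + 48/318.6 = 1.15.

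**4. Effect side (effects assumed).** Suppose the full package cuts mortality by one third, the hospital part alone by e, effects multiply, and the hospital effect is equal in both arms. The arm contrast is 1 − (2/3)/(1 − e). Full benefit over arm benefit is (1/3)/(1/3 − e).

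| e | arm contrast | full benefit / arm benefit |
|---|---|---|
| 0% | 33.3% | 1.00 |
| 5% | 29.8% | 1.18 |
| 10% | 25.9% | 1.43 |
| 20% | 16.7% | 2.50 |

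Steps 3 and 4 use different benchmarks (the between-arm ratio and the full-package ratio), so their factors must not be multiplied.

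**The case against.** **Costing.** Nothing says that hospital cost will be charged to the intervention arm. Both economic paragraphs speak of added resources and identify standard care with the control arm; a resource present in both arms is not added relative to that arm, so an incremental reading nets it out. Allocation could also sit in the SAP or a costing plan that is not at hand. This stands: mischarging is a risk, not a stated plan. It does not repair the comparator label.

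**Label.** By October 2019 an SBLP hospital is arguably part of existing care in the region, and section 4 speaks of a community programme. That is a possible reading, but it leaves the SBLP, defined to include the hospital, compared with a standard that already contains part of it. The text should say which is meant.

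**Cancellation.** A reader might infer that the hospital benefit cancels completely. The documents do not support that. It requires equal hospital use and benefit in both arms. If intervention HCs refer more or earlier, part stays in the difference, and section 8.1 already costs referral-hospital care if attendance rises. Survival benefit is also to be modelled, and the protocol does not say that the model uses only the arm contrast.

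**Referral.** The pathway in section 3 describes Cambodia generally, and no arm-specific referral flow is given for the province. Control access is inferred from that pathway and the single hospital: very probable, but not stated.

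**Magnitude.** The factors rest on assumed shares and effects. Headcount ignores equipment, meetings and travel. The background places most neonatal deaths in the community and around delivery, which lends no support to the 20% row.

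**Conclusion.** The point holds in this form. On the protocol's own dates and facility count, the control arm is very probably HC and village care without SBLP, backed by a referral hospital with it. The arm contrast estimates community SBLP added to that hospital. Describing it as SBLP against existing or normal care is not supported. Because cost is defined for the SBLP as a whole, the cost per DALY may combine full-package cost with a benefit that has lost some or most of the hospital effect. If so, the programme would look less cost-effective than it is. The factors of 1.11 to 2.00 on the cost side and 1.18 to 2.50 on the effect side show what assumptions would produce; they are not estimates.

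The disagreement between sections 3.2 and 8.1 on whose care costs count needs no assumption.

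A reader might also infer that the shared hospital undermines the mortality comparison or the one-third target. It does not invalidate the comparison: section 8.1 fixes a between-group analysis, and a shared background is acceptable once stated. The target is a separate, minor wording matter: if it means a province-wide change, the arm contrast does not estimate it, with or without a shared hospital.

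This should be corrected, at medium confidence. It concerns a tertiary objective and its interpretation, and the repair is cheap.

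**What to change.** - **Sections 3.2, 5 and 8.1:** define the comparator as control clusters with an SBLP-supported referral hospital, and match the wording in section 4 and the Synopsis. State the new referral hospital's opening date, which clusters it serves, and how referrals to it are treated.
- **Costing:** put hospital and HC/village components on separate lines. Keep hospital set-up cost common to both arms out of the trial-based increment, and count arm differences in hospital use. Report whole-package cost separately for the blueprint; a comparison of the full package with care before 2018 would need its own, explicitly modelled analysis.
- **Sections 3.2 and 8.1:** reconcile the lists of facilities (AHC, HCs, referral hospital) whose care costs are counted.
- **Synopsis and section 4:** say whether the one-third target is between arms or province-wide. If province-wide, state that the arm contrast does not estimate it and report the change descriptively.

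The cost is wording, one added fact about the new hospital, and one extra cost line; no new birth data are needed. The downside is a narrower claim: the arm effect and its cost per DALY no longer stand for the full village-to-hospital package.

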**Figure 1. Overview of the baby health meetings**

### ***Set-up***

The BHM will be conducted in the HCs chosen to be in the intervention group. Both prior to the meeting and after it refreshments will be served. The group will decide whether they want to sit on chairs or the floor. At the start of the first meeting ground rules will be discussed and agreed upon; these will be written in Khmer and displayed at each subsequent meeting. Flip charts, post it notes and pens will be available during each session to help clarify points and to reach consensus about topics. These charts will be photographed at the end of each meeting. All participants will receive their travel costs, calculated by distance travelled and at a fixed rate and paid at the end of the meeting.

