#### **Primary Outcome:**

1. Perinatal mortality rate will be described by hazard rate and 95% confidence interval (CI) separated by groups. Survival between groups will also be described using Kaplan-Meier plot. Log-rank test will be used for univariate comparison of survival. We will also describe median time to perinatal death with 95% CI in each group from Kaplan-Meier plot.

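### The study is labelled cluster randomised, but the only allocation rule in the protocol is purposive choice of health centres, with every other cluster as control

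*Protocol*

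**What the plan says.** The protocol claims randomisation in three places. The Study Design row of the Synopsis gives "Cluster randomised control trial". Section 5 opens with "A cluster randomised study design will be used", taking the health centre administrative group as the cluster. The sample size paragraph of Section 8.1 refers to "a simple parallel cluster randomised trial design".

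Section 5 then sets out how the arms are formed. Four clusters enter a pilot in July 2018 and ten enter the intervention arm in October 2019. The rest are covered by "Control arm: all remaining clusters". The rule for deciding which centre enters when is: "The choice of which health centres will be included at each time point will be made using purposive sampling". The aim is a mix of centres by distance to the referral hospital and by how many villages each one serves.

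Section 8.1 excludes the pilot from the primary analysis, which compares intervention with control clusters. For perinatal mortality it says "Log-rank test will be used for univariate comparison of survival" and refers to the SAP for full detail. The SAP was not available for this review.

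**The concern.** Purposive selection and random allocation are different mechanisms, and one set of clusters cannot have been assigned to arms by both. Because the controls are whatever is left over, choosing the intervention centres also settles the control arm. Judgement would then decide both sides of the comparison.

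Seeking variety among the chosen centres does not make the remaining ones comparable, either on the two named characteristics or on things nobody recorded, such as staff motivation, leadership or road access. Distance to the referral hospital could plausibly affect perinatal mortality in its own right.

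The main result at stake is the mortality comparison. Perinatal mortality is a secondary objective in the Synopsis and Section 4, but it is the primary outcome of the mortality analysis in Section 8.1 and carries the one-third reduction target. The economic evaluation also measures cost-effectiveness against the control arm, so it would inherit any selection bias.

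**Working it through.** **Textual check.** The protocol gives no figure to reproduce, because the point concerns mechanism. The question is whether any passage lets chance decide the arm.

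- Label: cluster randomised (Synopsis; Section 5; Section 8.1, sample size paragraph).
- Rule: purposive, applied at each time point (Section 5).
- Scope of the rule: Section 5 dates two cluster entries, the pilot and the October 2019 intervention arm. The rule therefore covers the arm that is analysed as well as the excluded pilot.
- Control arm: the complement of the chosen clusters (Section 5), so no pool of selected clusters is left to be randomised afterwards.
- Random sequence, draw, stratification or allocation concealment: none described anywhere in the protocol.
- Section 3.2, Set-up: "The BHM will be conducted in the HCs chosen to be in the intervention group". This wording is neutral, since a centre can be chosen at random, and nothing here rests on it.

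**Cluster count.** Section 3.3 says "Within the province there are 28 government HC, 17 HP". Assuming one cluster per health centre, which the protocol does not state, 28 − 4 pilot = 24 non-pilot clusters, and 24 − 10 intervention = 14 control.

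**Hypothetical illustration of scale.** Assumptions, none taken from the documents: equal births per cluster, 12 of the 24 clusters remote, remote mortality q times that of near clusters, and no intervention effect. With s1 and s0 the remote shares of the intervention and control arms, the rate ratio seen under no effect is

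RR = (1 + s1(q − 1)) / (1 + s0(q − 1))

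| Remote clusters, intervention v control | q = 1.3 | q = 1.5 |
|---|---|---|
| 5/10 v 7/14 | 1.150/1.150 = 1.00 | 1.250/1.250 = 1.00 |
| 4/10 v 8/14 | 1.120/1.171 = 0.96 | 1.200/1.286 = 0.93 |
| 6/10 v 6/14 | 1.180/1.129 = 1.05 | 1.300/1.214 = 1.07 |
| 3/10 v 9/14 | 1.090/1.193 = 0.91 | 1.150/1.321 = 0.87 |
| 7/10 v 5/14 | 1.210/1.107 = 1.09 | 1.350/1.179 = 1.15 |

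Read as a rate ratio between arms, the one-third reduction is 1 − 1/3 = 0.67.

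**What the illustration does not show.** A simple random draw of 10 from 24 has C(24,10) = 1,961,256 outcomes. Exact balance (5 remote, 5 near) arises in C(12,5)² = 792² = 627,264 of them, or 32%, so 68% of draws are unbalanced. A shift of one cluster either way takes 2 × 495 × 924 = 914,760 draws. A shift of two or more takes the remaining 1,961,256 − 627,264 − 914,760 = 419,232, or 21%. Chance alone therefore produces such splits often. The difference is that under random allocation their probability is known and a cluster-level analysis can account for it. Under purposive choice it is not known.

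**The case against.** The best defence is that the purposive sentence is left over from an earlier design. Section 8.1 says the design was changed and that adjustment for time is no longer made, which suggests that clusters once entered at several time points. On that reading the trial may have been randomised, with the SAP saying how. This is possible, and nothing here asserts that the actual allocation was non-random. But the sentence is current protocol text. A random step described in the SAP would still contradict it, and staff following Section 5 would select by judgement.

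A second reading is that purposive sampling only picks eligible clusters, which are then randomised. The text does not support this, because no later draw is described and unchosen clusters go straight to control.

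Three further points have some force:

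- Calling the log-rank test univariate leaves room for an adjusted analysis in the SAP, so a lack of adjustment cannot be held against the protocol. Adjustment would still not make the allocation random.
- The illustration concerns distance, which the purposive rule is meant to mix, and it cannot separate purposive from chance imbalance. It gives a sense of scale only.
- Perinatal mortality is formally a secondary objective. That narrows what is affected, but mortality is still the one outcome with a numerical target.

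**Conclusion.** The concern holds as written. The label and the only stated allocation rule contradict each other, and under that rule the mortality comparison is non-randomised. This must be fixed because it determines what causal claim the trial can make.

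The size of any bias cannot be derived from the documents, and its direction is open. The hypothetical range of 0.87 to 1.15 under no effect depends wholly on the assumed remote share, mortality ratio, equal births and one cluster per health centre. The conclusion depends on none of these. It rests only on the current text, and a documented random draw would turn the problem into one of wording.

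**What to change.** Which change applies depends on the state of allocation.

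- **Clusters not yet allocated.** Replace the purposive sentence in Section 5 with constrained or stratified randomisation of the non-pilot clusters, balanced on distance to the referral hospital and number of villages, and adjust for both in the analysis. State the total number of clusters (24, split 10 v 14, if each health centre is one cluster).
- **Clusters chosen purposively.** Replace the randomised wording in the Synopsis, Section 5 and Section 8.1 with non-randomised controlled cluster study. Adjust the primary mortality comparison for the two selection characteristics and, where available, for cluster mortality before the intervention. The protocol does not say that such baseline mortality is collected.
- **A random draw did take place.** Correct Section 5 to describe it.

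The cost is small. Each route needs an amendment submitted under Section 11.3. The first also needs one constrained draw, and the second needs three wording changes. The two covariates are already named in the protocol. With 24 clusters, adjusting for them reduces the cluster-level degrees of freedom from 24 − 2 = 22 to 20, or to 19 with baseline mortality. The real price of the second route is a weaker headline claim.

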#### **Secondary Outcomes:**

1. Description of the cohort
  - a. Prematurity
  - b. Birth weight
  - c. Sex
2. Facility based deliveries

Facility based deliveries prematurity, sex, will be described using percentage and compared between groups using Chi-square test or Fisher's exact test as appropriate. Number of ANC visits will be described using median with inter-quartile range (IQR) and compared between groups using Mann-Whitney U test. Birth weight will be described using mean with standard deviation and compared between groups using Student's t test or using median with inter-quartile range and compared between groups using Mann-Whitney U test if data have non-normal distribution.

Statistical analysis will be performed using STATA software package. Statistical significance will be considered if  $p$ -value  $< 0.05$

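### No between-group comparison named in the protocol accounts for the two characteristics used to choose clusters, so any arm imbalance on them would enter the mortality and facility-delivery results

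*Protocol*

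**What the plan says.** Protocol section 5 (Study Design) opens by calling the design cluster randomised: "A cluster randomised study design will be used, with a cluster being defined as a HC administrative group". It then says that the choice of health centres at each time point "will be made using purposive sampling to ensure a mix of health centre characteristics". The factors are named: "Characteristics that will be taken into account are the distance from the health centre to the referral hospital and number of villages the HC serves".

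The groups are filled in sequence:

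- "Pilot: to begin in July 2018, consisting of 4 clusters"
- "Intervention arm: to begin October 2019, consisting of 10 clusters"
- "Control arm: all remaining clusters"

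Section 8.1 names the comparisons. For perinatal mortality (Primary Outcome), besides hazard rates and Kaplan-Meier curves by group: "Log-rank test will be used for univariate comparison of survival". For facility deliveries, prematurity and sex (Secondary Outcomes), the data "will be described using percentage and compared between groups using Chi-square test" or Fisher's exact test. Birth weight gets a t test or Mann-Whitney U test. The only adjustment mentioned is for time, in the Sample size Calculation subsection, and only to say that it is dropped. That subsection also excludes the pilot clusters from the primary analysis and refers to the SAP, which is not available here, for full details.

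**The concern.** An unadjusted two-group test relies on random allocation to make the arms comparable. Section 5 describes a purposive choice on two known factors and seeks the mix in the clusters chosen. Nothing is done to make the remainder resemble them.

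Distance plausibly matters for both outcomes. The Background section says that babies born at health centres or health posts who need further care are sent to the referral hospital, so remoteness may affect survival as well as place of delivery. Section 5 also brings the programme into that hospital in 2018, before the intervention arm starts in October 2019. Clusters in both arms can refer to a hospital that already has the programme, and access to it may depend on distance. The number of villages served plausibly tracks births per cluster, and so each cluster's weight in an individual-level test.

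If the arms differ on either factor, the named tests cannot separate that difference from the effect of the programme. The distortion could go in either direction.

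**Working it through.** The protocol gives no power, event-rate or imbalance figure for this comparison, so there is nothing to reproduce. The check asks how large the distortion could be when the programme has no effect.

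**Inputs from the protocol.** 28 health centres (section 3.3); 4 pilot and 10 intervention clusters, remainder control (section 5); pilot excluded from the primary analysis (section 8.1); target of a one-third reduction, a ratio of about 0.67 (section 4).

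**Assumptions.** One cluster per health centre (the number of administrative groups is not stated), giving 28 − 4 = 24 clusters in the analysis and 24 − 10 = 14 controls. Clusters classed as near or far. Equal births per cluster. Event rate in far clusters *r* times that in near ones, with *r* from 1.3 to 1.5.

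**Formula.** With *a* near and *b* far clusters in the intervention arm (*a* + *b* = 10), and *c* near and *d* far in control (*c* + *d* = 14):

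null rate ratio = [(*a* + *b·r*)/10] ÷ [(*c* + *d·r*)/14]

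| Near/far among 24 | Meaning of mix | Intervention near/far | Control near/far | *r* = 1.3 | *r* = 1.5 |
|---|---|---|---|---|---|
| 8/16 | equal quota | 5/5 | 3/11 | 1.150/1.236 = 0.931 | 1.250/1.393 = 0.897 |
| 12/12 | equal quota | 5/5 | 7/7 | 1.000 | 1.000 |
| 16/8 | equal quota | 5/5 | 11/3 | 1.150/1.064 = 1.081 | 1.250/1.107 = 1.129 |
| 8/16 | proportional | 3/7 | 5/9 | 1.210/1.193 = 1.014 | 1.350/1.321 = 1.022 |
| 16/8 | proportional | 7/3 | 9/5 | 1.090/1.107 = 0.985 | 1.150/1.179 = 0.976 |

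**Reading the table.** Under the equal quota with 8 near and 16 far, a programme with no effect would show a 7% to 10% reduction. That is about a fifth to a third of the one-third target (6.9/33.3 = 0.21; 10.3/33.3 = 0.31). With 16 near and 8 far, a true ratio of 0.667 would appear as 0.667 × 1.081 = 0.72 to 0.667 × 1.129 = 0.75. Under a proportional mix the distortion is about 2% at most.

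**Wider range.** If the pilot is also filled by equal quota (2/2) and *r* runs from 1.25 to 2.0, the null ratio is 0.91 to 0.78 when 20 of the 28 centres are far, and 1.11 to 1.40 when 8 are far. Proportional quotas in both pilot and intervention keep it between 0.97 and 1.03 in every split run.

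No comparable figure is offered for villages served, because the protocol gives nothing on how it relates to the outcomes.

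**The case against.** The strongest objection is that covariate adjustment is normally SAP material, that section 8.1 refers to the SAP for full details, and that calling the log-rank test univariate leaves room for a further adjusted model. This stands in part. A reader might infer that the two factors enter no analysis of the trial at all; the documents do not support that, and the claim is limited to the comparisons the protocol names. The objection does not dispose of the point. The protocol itself fixes the tests and the 5% threshold, and for facility deliveries the unadjusted test is the only comparison stated.

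The second objection is that section 5 asks for a mix, not for equal halves. A reader might infer that the selection rule itself unbalances the control arm. That holds only when the mix departs from the distribution among the available clusters. The protocol reports no such distribution, and a proportional mix nearly removes the problem. This objection stands: imbalance is a possibility, not a finding.

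Third, the figures also rest on equal births per cluster, which is unlikely when the number of villages served varies. And where the distortion runs against the programme, it would attenuate the target effect (to about 0.72 to 0.75) rather than hide it. Both are accepted.

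Finally, the conflict in section 5 between a randomised label and a purposive choice is the larger defect, and this point partly follows from it. That is so, but correcting the label would leave the named comparisons unadjusted for known selection factors.

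**Conclusion.** The point holds in limited form. The protocol selects clusters on two named factors, leaves control as an unmatched remainder, and names only comparisons that ignore both factors. Any arm imbalance on them would go into the results for perinatal mortality and facility deliveries.

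The size is conditional. Under an equal near/far quota the illustrative null ratio runs from about 0.90 to 1.13; under a proportional mix, from about 0.98 to 1.02. Both ranges assume one cluster per health centre, equal births per cluster, the near/far splits shown and a far/near rate ratio of 1.3 to 1.5. None of these comes from the protocol. The documents show neither that the arms are unbalanced nor that the trial's result would be biased. The weakness is that the protocol neither excludes imbalance by its selection rule nor corrects for it in the analysis it states.

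**What to change.** In section 8.1, state that the main between-arm comparison of perinatal mortality and of facility deliveries is a cluster-level analysis or a cluster-aware regression, adjusted for distance to the referral hospital and number of villages served. Define distance as measured when clusters were selected, because section 5 brings a new referral hospital into the programme in 2022. Tabulate both factors by arm. Keep the unadjusted tests as secondary results. Cohort descriptors such as sex can stay descriptive. If the SAP already contains such a model, section 8.1 should name it as the main comparison.

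No new data are needed, since both values are required to select the clusters. The cost is wording plus about two cluster-level degrees of freedom: from about 22 (24 clusters less two arm means) to about 20, on the one-cluster-per-centre assumption. Adjustment deals with these two factors only. It does not replace randomisation, and the conflict in section 5 between randomised and purposive allocation must be resolved separately.
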